To further define the impact of NP in the peripartum period, we propose the following objectives:

- I. Characterize the course and pharmacological management of neuropathic pain in pregnancy and the postpartum period. We will define descriptive statistics of the use of analgesic medications in pregnancy and the postpartum period for the treatment of neuropathic pain.
- II. Compare obstetrical and neonatal outcomes of pregnant women with chronic neuropathic pain, non-neuropathic chronic pain, and pregnant women without chronic pain.
- III. Determine the acceptability and tolerability of rTMS for the treatment of neuropathic pain in pregnancy, and describe the impact of rTMS on neuropathic pain in pregnancy.

Subject Selection

Subjects will be enrolled through the Women's Mental Health Program (WMHP) at the University of Arkansas for Medical Sciences (UAMS) at the following clinical spaces: Psychiatric Research Institute (PRI); UAMS Women's Clinic (UWC); the Psychiatric Research Institute (PRI) inpatient units (PRI floors 5&6); and the UAMS Obstetrics & Gynecology units (UAMS floors 5,6, and 7A).

Protocol Title: Neuropathic Pain in Pregnancy
Institution: University of Arkansas for Medical Sciences (UAMS)
IRB Number: 204737
Sponsor: UAMS
PI: [name]

Study visits can occur at all of the above locations. For those subjects in part B, study visits will occur in a designated room designed for rTMS in the PRI. We aim to actively recruit and enroll 60 pregnant women and up to 70 infants (to allow for multiple gestation pregnancies) for Part A of this study and enroll 10 pregnant women and up to 15 infants (to allow from multiple gestation pregnancies) (from Part A) for Part B.

Compensation: Mothers participating in the study will receive a \$10 in cash for each visit. All participants will be given a token or voucher to pay for parking at each outpatient study visit when applicable.

Inclusion of Women, Minorities and Children

Women and adolescents between 18-45 years of age are eligible for participation in the current study. Every effort will be made to recruit a diverse population of women along racial and ethnic categories residing in underserved areas.

Eligibility Criteria

All women will provide consent and HIPAA authorization prior to enrollment in the study.

Part A:

Maternal Inclusion Criteria

- Age 18-45 years old,
- Ability to give informed consent,
- Viable pregnancy, and
- Enrollment prior to or equal to 24 weeks gestation

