Maternal Exclusion Criteria

- Active or history of substance use disorder within the past year
- Non-English speaking

Part B:

Maternal Inclusion Criteria

- Subjects enrolled in Part A and willing to consent to Part B of this protocol
- Pregnant with current chronic neuropathic pain
- Subjects failed treatment with amitriptyline or nortriptyline as defined by one of the following:
 - no clinical improvement following a four week trial of amitriptyline or nortriptyline (i.e., CGI-I score ≥ 4)
 - an inability to tolerate the medication (i.e., side effects)
- Subjects must pass the TMS Safety Checklist Adult Safety Screen (TASS).
- Subjects should be off medication, which can lower seizure thresholds (e.g., amitriptyline and nortriptyline) for at least two weeks prior to study entry.
- Subjects with neuropathic pain including those with diagnosis of spinal cord injury, fibromyalgia, compression neuropathies (including diabetic peripheral neuropathy), post stroke pain, and multiple sclerosis
- Subjects with a baseline VAS score greater than 30

Protocol Title: Neuropathic Pain in Pregnancy
Institution: University of Arkansas for Medical Sciences (UAMS)
IRB Number: 204737
Sponsor: UAMS
PI: [name]

Maternal Exclusion Criteria

- Current or past history of a seizure disorder (e.g., epilepsy)
- Current history of preeclampsia
- Current or history of brain lesions (e.g., aneurysm)
- History of major head trauma (e.g., stroke; previous cranial neurosurgery)
- Ferromagnetic metal in the head, neck, or chest (e.g., plates or pins, bullets, shrapnel)
- Microprocessor implants in the head (e.g., cochlear implants) or life-sustaining microprocessor implants anywhere in the body (e.g., prosthetic cardiac valves)
- Cardiac pacemaker
- Active or inactive implants (e.g., deep brain stimulators, vagus nerve stimulators)
- Active treatment with medications that lower seizure threshold (e.g., bupropion, amitriptyline, nortriptyline, or other TCA)
- Increased intracranial pressure (which lowers seizure threshold)
- Implanted medication pumps
- Intracardiac lines
- Significant heart disease defined as heart disease that causes moderate to severe symptoms and/or is characterized by moderate to severe pathology, including a recent history of myocardial infarction and heart failure with an ejection fraction of less than 30% or with a New York Heart Association Functional Classification of Class III or IV.
- Bipolar disorder (to reduce the risk of mania)

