- History of suicide attempt(s)
- Family history of epilepsy
- Heavy alcohol consumption within the past 48 hours
- Permanent makeup or tattoos with metallic dyes

Investigational Plan

The study will involve two phases - initially focusing on identification and course, followed by treatment paradigm assessment (Part A), and culminating in a pilot trial of rTMS (Part B).

Part A:

Study visits will occur approximately every 4-6 weeks during pregnancy until approximately 3 months postpartum for a maximum of 12 visits. Table 1 provides an overview of study procedures. Figure 1 illustrates subject participation and flow. In order to optimize diagnostic clarity for group assignment, we will employ a valid tool, the painDETECT Questionnaire (PDQ), for diagnostic purposes (written permission for use of PDQ has been obtained and is available upon request). The PDQ has been validated and shown high sensitivity (85%), specificity (80%), and positive predictive value (83%) (Freynhagen *et al* 2006). At study entry, subjects will complete the PDQ. Based on their scores, subjects will be separated into three groups: Group 1) subjects with NP in pregnancy (score ≥ 13); Group 2) subjects with non-neuropathic pain in pregnancy ($1 \geq \text{score} \leq 12$); and Group 3) subjects without any type of pain in pregnancy (score=0).

Other measures collected at entry include a general biographical form (WMHP Intake Form). Subjects will complete pain measures and the Beck Depression Inventory (BDI) (Beck *et al* 1960) at study entry and at each study visit. Pain measures include the Visual Analogue Scale (VAS), Pain Catastrophizing Scale (PCS) (Sullivan *et al* 1995), and measures of pain intensity, pain interference, pain behavior - all three derived from Patient Reported Outcomes Measurement Information System (PROMIS) (Amtmann *et al* 2010; Revicki *et al* 2009; Cella *et al* 2010). At each visit, the exposure tracking form will record the timing (weeks of gestation) and dosage of all

Protocol Title: Neuropathic Pain in Pregnancy
Institution: University of Arkansas for Medical Sciences (UAMS)
IRB Number: 204737
Sponsor: UAMS
PI: [name]

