prescription and non-prescription medications used in pregnancy and the postpartum period. A urine drug screen will also be obtained at each visit testing for the presence or absence of the following: amphetamines/methamphetamines, barbiturates, benzodiazepines, THC, cocaine, methadone, opiates, PCP, and cotinine. For all visits following entry visit, subjects will complete the Patients' Global Impression of Change scale (PGIC) (Hurst and Bolton 2004); and the clinician will complete the Clinical Global Impression-Global Improvement scale (CGI-I) (Guy 1976). At all study visits, weight and vital signs will be collected. For all subjects who delivered at UAMS, medical records for labor and delivery and neonatal outcome will be obtained following birth. All subjects will participate in Part A. All subjects will receive treatment as usual within each group.

Part B:

Subjects in group 1 will be invited to participate in part B of the study following their enrollment in part A. This pilot study will aim to enroll 10 subjects (of Group A).

Subjects will undergo daily rTMS, defined as Monday through Friday, for a total of 10 consecutive sessions with the exception of weekends and holidays (i.e., Monday to Friday only). Typically, a stimulation period will start on Monday (day 1) and end on Friday (day 12). In the case that a stimulation period does not start on Monday, day 1 will begin on the day of the subject's first rTMS session. Subjects will be followed daily until day 29, following their last session of rTMS (day 12). Table 2 provides an overview of study procedures. For each session (days 1-5 and 8-12), subjects will complete a VAS prior, immediately following, and 60 minutes post. Adverse events will also be recorded prior to and immediately following and 60 minutes after each session. They will complete a BDI on Days 1, 5, 12, 22, and 29. Subjects will complete VAS also on days 22 and 29. For days 5, 12, 22, and 29; subjects will complete the PGIC; and clinicians will complete the CGI-I. Subjects will have a maximum of 12 visits for Part B (10 rTMS sessions plus days 22 and 29). Either study visit for days 22 or 29 may occur in conjunction with a study visit for Part A.

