
• Preterm labor• Preterm birth• Premature rupture of membranes• Mode of delivery	
• 1 minute and 5 minute APGAR Scores• Length of Hospitalization• Neonatal Intensive Care Unit Admission• Neonatal Abstinence Syndrome• Birth weight and length• Gender

Part B (rTMS):

We will determine the acceptability of rTMS as a treatment option by determining the percentage of subjects who accept the treatment when offered. Tolerability will be determined by the reporting of adverse events. The primary outcome measure is VAS. Secondary outcome measures include BDI, PGIC, and CGI-I. For each outcome measure, scatter plots will be constructed for visual inspection across treatment. Using previous studies of rTMS for the treatment of neuropathic pain, we will determine an effect size and complete a power analysis. This information will help guide future studies of the effectiveness of rTMS in the treatment of neuropathic pain in pregnancy.

Neonatal outcomes will be analyzed between the following groups: 1. Subjects participating in rTMS (Part B); 2. Subjects with neuropathic pain who participated in Part A but did not participate in Part B; 3. Subjects with chronic non-neuropathic pain who participated in Part A; and 4. Subjects without chronic pain who participated in Part A. Specific endpoints of interest include neonatal intensive care unit admission, length of hospitalization, birth weight and length, and 1-min and 5-min APGAR scores. The occurrence of obstetrical outcomes will be compared between the groups. If measures are normally distributed, we will use ANOVA to test the differences among the three groups. Otherwise, we will use a non-parametric method, such as Kruskal Wallis test, to test the difference among the groups.

Neonatal outcomes will be scrutinized after each delivery and neonatal period. The investigator team will convene and review all neonatal outcomes to determine if any complication occurred that could be attributed to the study, participation in the study, and/or treatment received. If any complication is identified (i.e. preterm delivery with all subjects who participated in rTMS), we will cease all current and potential study procedures related to part B of the study.

All statistical analysis will be completed using SAS 9.4. Significance will be set at $p<0.05$.

Data Safety and Monitoring Plan

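### The neonatal comparison of rTMS women with other neuropathic women cannot separate an rTMS effect from Part B eligibility and background drugs

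*Protocol*

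**What the plan says.** The Part B text under Statistical Methods and Data Management is the same in the protocol and the SAP. It lists four groups for neonatal outcomes: the rTMS women; "Subjects with neuropathic pain who participated in Part A but did not participate in Part B"; women with chronic non-neuropathic pain; and women without chronic pain. The endpoints are NICU admission, hospital stay, birth weight and length, and the two APGAR scores. The test is ANOVA or Kruskal-Wallis at p<0.05. It is described as a test of three groups although four are listed, which needs reconciling. No pairwise contrast, covariate, matching or restriction is given.

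Women reach the first two groups as follows.

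- Protocol, Subject Selection: "We aim to actively recruit and enroll 60 pregnant women" for Part A. No size is given for any pain group.
- Protocol, Investigational Plan, Part A: Group 1 is "subjects with NP in pregnancy (score ≥ 13" on the painDETECT questionnaire at entry. On treatment: "All subjects will receive treatment as usual within each group".
- Protocol, Investigational Plan, Part B: "Subjects in group 1 will be invited to participate in part B of the study following their enrollment in part A", and "This pilot study will aim to enroll 10 subjects". Nothing is randomised.
- Protocol, Eligibility Criteria, Part B, inclusion: "Subjects failed treatment with amitriptyline or nortriptyline as defined by one of the following" (no improvement after a four-week trial, or intolerance), and a baseline VAS above 30.
- Protocol, Eligibility Criteria, Part B, exclusion: "Active treatment with medications that lower seizure threshold (e.g., bupropion, amitriptyline, nortriptyline, or other TCA", together with seizure disorder, family history of epilepsy, bipolar disorder, past suicide attempt, significant heart disease, current preeclampsia, brain lesions, various implants and others.

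**The concern.** Group 2 is the only comparison group that shares the rTMS women's pain category, so a reader will use it as the reference for rTMS. It is defined by not entering Part B. A Group 1 woman who fails any Part B criterion falls into it automatically, beside women who declined and any left over once the places are filled.

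The two groups can therefore differ in maternal disease, pain severity and drug treatment before any stimulation is given. The protocol's own background text, before Objectives, attributes neonatal abstinence syndrome to opioids, antidepressants and muscle relaxants used for neuropathic pain. That syndrome is not among the Part B neonatal endpoints, but it could plausibly act through NICU admission and hospital stay, which are. At stake is whether a difference, or its absence, can be read as evidence on the neonatal safety of rTMS.

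**Working it through.** **1. Side-by-side reading of the criteria**

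| Feature | rTMS women | Other Group 1 women |
|---|---|---|
| Part A criteria (age, viable pregnancy, entry by 24 weeks, no substance use disorder in the past year, English-speaking) | required | required |
| painDETECT score 13 or more | required | required |
| Amitriptyline or nortriptyline | failed or not tolerated | never given, responding, or failed |
| Baseline VAS | above 30 | any |
| Drugs that lower seizure threshold | stopped at least two weeks before entry | any |
| Seizure disorder, bipolar disorder, suicide attempt, significant heart disease and the rest of the list | barred | allowed |
| Opioids, muscle relaxants, antidepressants that do not lower seizure threshold | not barred | not barred |

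Rows three to six differ by design. The last row does not.

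**2. How much of the comparator could be ineligible**

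The documents give no Group 1 size, eligible share, uptake, event rate or power for this comparison, so there is no figure to reproduce. What follows is illustration on assumed inputs: Group 1 size G, eligible share e, and uptake among eligible women u of 50%, 75% or 100%. Only the target of 10 comes from the protocol.

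- Women entering Part B: B = min(10, G·e·u)
- Ineligible share of the comparator: f = G(1−e) / (G−B)

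Example: G = 20 (one third of 60), e = 0.6, u = 0.75. Eligible 12, B = 9, comparator 11, ineligible 8, so f = 8/11 = 73%.

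| G | e = 40% | e = 50% | e = 60% | e = 75% |
|---|---|---|---|---|
| 20 | 75–100% | 67–100% | 57–80% | 40–50% |
| 30 | 75–90% | 67–75% | 57–60% | 38% |
| 40 | 75–80% | 67% | 53% | 33% |

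**3. Difference produced with no rTMS effect**

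Assume that rTMS women carry the same risk as untreated eligible women. The difference (rTMS minus comparator) is then f × (risk in eligible − risk in ineligible). At f = 0.75, with assumed NICU risks:

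- 10% eligible, 30% ineligible: comparator risk 0.75×30 + 0.25×10 = 25%; difference −15 points. A true rTMS risk ratio of 25/10 = 2.5 would be hidden.
- 10% eligible, 20% ineligible: 0.75 × (10−20) = −7.5 points.
- 20% eligible, 10% ineligible: 0.75 × (20−10) = +7.5 points, so the sign reverses.

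**4. What remains if the comparator is split**

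Eligible non-participants number G·e − B. For e of 40% to 60% that is 0 to 6 women with G = 20 and 2 to 9 with G = 30. The smallest standardised difference detectable with 80% power (two-sided 0.05) is (1.96+0.84) × √(1/n₁+1/n₂): 1.25 for 10 versus 10 and 1.53 for 10 versus 5. Neither the pooled nor the split comparison can support more than description.

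**The case against.** The strongest reply is that little rests on this comparison. Objective III concerns acceptability, tolerability and a description of impact; the Part B primary outcome is VAS; no pairwise test of rTMS against Group 2 is named. Stopping rests on review of each delivery, and the medical monitor reviews adverse events after every three enrolments. With 10 versus 10 and an assumed NICU risk of 20%, the 95% margin is about 1.96 × √(2×0.2×0.8/10) = ±35 points, wider than the distortions above. All of this stands and limits the consequence. It does not remove the problem: the plan still sets p<0.05, and small numbers do not cure a systematic difference.

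Four stronger readings are tempting, and the documents do not support them.

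- *The comparator is filtered only by painDETECT.* The Part A criteria apply to everyone, including the substance use exclusion, which bears on neonatal drug exposure.
- *The comparator has more antidepressant exposure.* Part B women must have tried a tricyclic, possibly in this pregnancy; usual treatment covers them too; other antidepressants and opioids are not barred as such; and nothing says that tricyclics stay stopped until delivery. The difference is one of type and timing.
- *The comparator is mostly women barred from rTMS.* That depends on figures the documents do not give. It holds in every scenario above with at most 60% eligible, and in none at 75%.
- *The contrast measures eligibility instead of rTMS.* A real rTMS effect would still be in it; it just cannot be separated out.

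A formal test against eligible non-participants alone would also be a poor remedy, given how few there may be.

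**Conclusion.** The point holds as a confounded comparison. Following the plan as written sets rTMS women, who passed the Part B criteria, against a mixture of eligible and ineligible women, with no restriction or adjustment. Neither a difference nor its absence can be attributed to rTMS. The direction is unknown: serious maternal disease in the comparator could make rTMS look safer, while milder or drug-responsive pain there could make it look worse.

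The size is conditional. Across the assumed inputs the ineligible share runs from 33% (G = 40, 75% eligible) to 100% (G = 20, 40% or 50% eligible with full uptake). The resulting difference depends on risk gaps that the documents do not give. The case-by-case stopping review is not affected, nor are the VAS, acceptability and tolerability analyses.

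**What to change.** In the Part B text of both documents:

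1. For each Group 1 woman, flag whether she met the Part B criteria other than willingness to consent, with a stated rule for the visit at which this is judged. Record which criterion failed and the reason for not taking part: ineligible, declined, places filled, or not offered.
2. Show neonatal outcomes for rTMS women, eligible non-participants and ineligible women, separately and with the last two pooled.
3. Tabulate tricyclic, other antidepressant, opioid and muscle relaxant exposure by group.
4. Report differences with confidence intervals as descriptive, with no p<0.05 test and no comparative statement on rTMS safety. Reconcile the three-group and four-group wording.

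The cost is wording, one flag and split tables. Intake history, medical records, VAS, CGI-I and the exposure form are already collected in Part A, and the acceptability percentage already requires a count of offers and acceptances.

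The downside is imprecision. Eligible non-participants will probably be very few, partly because women not planning rTMS have little reason to be off the barred drugs. Some criteria may be unknown for some women. The Initial Screening section mentions TASS, but Table 1 does not list it for Part A. CGI-I rates change since the last study visit, so it cannot document a tricyclic failure before Part A. Such women should be shown as having unknown eligibility.

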Patients will be informed that they have the right to withdraw from the study at any time for any reason, without prejudice to their medical care. The Principal Investigator also has the right to withdraw subjects from the study for any of the following reasons:

- In the event of a seizure or other AE
- Non-compliance
- Protocol violation
- Study terminated
- At discretion of PI

Risks and Benefits

Identification of Adverse Events:

An adverse event is defined as any new medical problem, or exacerbation of an existing problem, experienced by a subject while enrolled in the study, whether or not it is considered drug/device-related by the investigator.

Adverse Event Reporting

All adverse events occurring during the course of the study, whether related to Part A or Part B or otherwise, will be recorded on the Adverse Event Case Report Form. For all adverse events, the Investigator will provide an assessment of the adverse event, its treatment and resolution, and its relationship to the study. Special reporting procedures are required for certain adverse events.

Relationship of Adverse Events to the Investigational Device

The investigator will assess the relationship of the adverse event to the investigational device. The relationship will be assessed using the following categories:

- Definitely Related: A direct cause and effect relationship between the investigational drug or device/experimental treatment and the adverse event exists.
- Possibly Related: A direct cause and effect relationship between the investigational drug or device/experimental treatment and the adverse event has not been clearly demonstrated, but is likely or very likely.
- Unlikely Related: A direct cause and effect relationship between the investigational drug or device/experimental treatment and the adverse event is improbable, but not impossible.
- Unrelated: The adverse event is definitely not associated with the investigational drug or device/experimental treatment.

Unanticipated Adverse Device Effects

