If serious adverse event occurs, the investigator will promptly notify the sponsor of such an event within 24 hours of first learning of the event using the FDA MedWatch 3500A form. The can be found on-line at: <https://www.fda.gov/media/69876/download>

The investigator will also promptly notify the IRB of such an event as soon as possible, but no later than ten (10) working days after first learning of the event.

Severity

Each adverse event will be assessed for its severity, or the intensity of an event experienced by the subject, using the following.

- Mild: Discomfort noticed, but no disruption to daily activity.
- Moderate: Discomfort sufficient to reduce or affect normal daily activity.
- Severe: Inability to work or perform normal daily activity.

Deaths

The investigator will notify the sponsor and IRB as soon as possible, preferably within 24 hours but in no event later than 48 hours, of learning of subject's death, regardless of whether the death is related or unrelated to the investigational drug or device. The investigator will attempt to determine, as conclusively as possible, whether the death is related to the drug or device. The cause of death and the investigator's discussion regarding whether or not the death was drug- or device-related will be described in a written report.

Pre-existing conditions

Pre-existing conditions will not be reported as an adverse event unless there has been a substantial increase in the severity or frequency of the problem, which has not been attributed to natural history.

Protocol Title: Neuropathic Pain in Pregnancy
Institution: University of Arkansas for Medical Sciences (UAMS)
IRB Number: 204737
Sponsor: UAMS
PI: [name]

Eliciting and Reporting Adverse Events

The investigator will assess subjects for the occurrence of adverse events at each study visit. All adverse events (serious and non-serious) reported by the subject will be recorded on the source documents and CRFs.

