Facial numbness and facial nerve stimulation may also occur. Some sources estimate that 1 out of 3 individuals experience "facial twitching" during and/or after rTMS sessions. This twitching in the facial muscles is caused by intense electrical stimulation that penetrates the cortex. We will minimize this risk by using as conservative stimulation parameters as possible to meet the goals of the study.

Some patients may have fainted (syncopal/convulsive syncopal) or become lightheaded and nauseous during rTMS. We would stop TMS in case of suspected syncope. Such symptoms have been brief and resolved completely. In order to minimize risks the study doctor or nurse will use the following procedures to minimize the risks of convulsive syncope:

- Request information regarding a history of syncope during your screening process
- Monitor blood pressure during rTMS
- Monitor you for signs and symptoms of syncope appearing during rTMS and stop stimulation if signs and/or symptoms occur
- Immediately place you in a reclining position elevating your legs if signs or symptoms of syncope appear

Temporary changes in mood, such as mania and hypomania, have been caused by rTMS with high frequency stimulation. There are no reports of lasting changes in mood using the rate of stimulation that will be used in this study. To minimize this risk, subjects with a history of bipolar disorder have been excluded from participation in the study. In addition, subjects will be assessed clinically by the PI daily after each rTMS session for the development of mania or hypomania. If they develop during the study, the subject will be withdrawn from the study and referred for appropriate treatment as indicated. The PI is trained in the assessment and treatment of hypomania and mania.

Ferromagnetic pigments may interfere with rTMS treatments, and some forms of eye make-up, especially eyeliner, eye shadow and mascara, may contain ferromagnetic pigments. To minimize this occurrence, all subjects will be asked to remove all forms of eye makeup before each rTMS treatment.

The long-term effects of rTMS are unknown.

There may be benefit to subjects in this study who are participating in rTMS. For all others, taking part in this research study may not benefit the subjects personally, but we may learn new things that may be of benefit to women and children in the future.

References:

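### Withdrawal for an adverse event is worded as leaving the study, with no separate status for stopping rTMS, so later maternal follow-up ends and the position of delivery and neonatal records is left unstated

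*Protocol*

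**What the plan says.** Two places in the Protocol govern how a woman leaves.

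- *Termination of Study Participation*: "The Principal Investigator also has the right to withdraw subjects from the study for any of the following reasons". The first reason listed is "In the event of a seizure or other AE". This is a right of the investigator, not a duty. It is not limited by severity or by relation to the device.
- *Risks Associated with rTMS (Part B)*, on mania and hypomania: "If they develop during the study, the subject will be withdrawn from the study and referred for appropriate treatment as indicated". This one is mandatory.

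Two more fix when adverse events are captured. *Identification of Adverse Events* defines an event as a new or worsened problem "experienced by a subject while enrolled in the study, whether or not it is considered drug/device-related by the investigator". *Eliciting and Reporting Adverse Events* adds: "The investigator will assess subjects for the occurrence of adverse events at each study visit".

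Delivery and infant data follow a different route. The *Investigational Plan* for Part A states: "For all subjects who delivered at UAMS, medical records for labor and delivery and neonatal outcome will be obtained following birth". *Access to Medical Records* bases that access on the informed consent and says infants are assessed through records only. The Part B statistical section, identical in the SAP, says of the safety review: "The investigator team will convene and review all neonatal outcomes to determine if any complication occurred". It defines the rTMS group in the neonatal comparison as subjects participating in rTMS.

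**The concern.** Objective III is the acceptability and tolerability of rTMS in pregnancy, and tolerability is to be read from adverse event reports. The team also reviews neonatal outcomes after each delivery and ceases Part B if it finds a complication attributable to treatment. Both uses need data on every exposed pregnancy, including those in which treatment was stopped.

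On the plain wording, the event that ends treatment can also end observation. rTMS is given during pregnancy, so such a withdrawal normally comes before delivery. The women whose follow-up is cut short would then be selected by a safety event. The background section itself notes that a seizure can harm a pregnancy. For a seizure or other event, the decision to withdraw is also made case by case after the event is known, so the completeness of follow-up may depend on how the event was seen.

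**Working it through.** **Step 1. What happens to each kind of data if a Part B woman is withdrawn from the study**

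- *The triggering event*: kept. *Adverse Event Reporting* requires all events to be recorded, with treatment, resolution and relationship assessed.
- *Later maternal adverse events*: not captured. They fall outside the enrolled period, and the visits at which they would be elicited have ended. Table 2 marks adverse events only on session days, so later capture depends on the general rule for study visits.
- *Day 22 and 29 measures (VAS, BDI, PGIC, CGI-I)*: no provision after withdrawal.
- *Part A visits, every 4-6 weeks to about 3 months postpartum*: no provision after withdrawal.
- *Delivery and neonatal records*: not stated either way. They need no visit and are to be obtained for all who deliver at UAMS, but the visible text does not say whether record access outlasts a withdrawal.
- *Analysis group*: not stated for women who stop early.

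**Step 2. Size**

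The documents give no dropout rate, power or sample-size formula behind the 10 women, so there is no figure to reproduce. The input from the plan is n = 10 (*Subject Selection*). The number lost (0 to 3) and one infant per woman are assumptions.

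- Share per woman: 1/10 = 10%.
- One adverse infant outcome in a withdrawn woman, exact (Clopper-Pearson) 95% intervals: 1/10 = 10% (0.3% to 44.5%) if collected; 0/9 = 0% (0% to 33.6%) if not.
- One-sided 95% upper bound when no events are seen, 1 − 0.05^(1/n): 25.9% (n = 10), 28.3% (n = 9), 31.2% (n = 8), 34.8% (n = 7).
- Chance of seeing at least one event at an assumed true rate of 10%, 1 − 0.9^n: 65.1%, 61.3%, 57.0%, 52.2% for the same n.

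The last two lines treat loss as unrelated to outcome. The main worry is loss that is related to outcome, and the 1/10 versus 0/9 line shows that case.

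**Step 3. How likely is a withdrawal?**

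The chance that at least one of 10 women is withdrawn is 1 − (1 − w)^10. For an assumed w of 5%, 10%, 20% or 30% this is 40.1%, 65.1%, 89.3% or 97.2%, with 0.5, 1, 2 or 3 women expected.

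The Protocol's own figures bear on how often a ground for withdrawal could arise:

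- Seizure, at most 1/10,000: 10 × 1/10,000 = 0.1% across 10 women, or about 1% if read per session (100 sessions).
- Head and neck pain, about 10%: 1 − 0.9^10 = 65.1% for at least one of 10.
- Facial twitching, up to 1 in 3: 1 − (2/3)^10 = 98.3%.

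Seizure is thus very unlikely here, while the phrase covering any other adverse event will very probably be met. Meeting it permits withdrawal; it does not make withdrawal likely.

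**The case against.** The strongest reply is that the text says less than it may seem to, and much of this stands.

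- A reader might infer that any woman with a seizure or adverse event must leave. The documents do not support that: only mania or hypomania carries a mandatory withdrawal. Against that trigger, bipolar disorder is excluded from Part B, and the Protocol reports no lasting mood changes at this stimulation rate.
- A reader might infer that her infant's outcome is lost. No text excludes it. Infants are assessed from records, access comes with the original consent, and the review is of all neonatal outcomes. These provisions point towards collection.
- A reader might infer that the safety review would rest only on women who tolerated rTMS. It would not, because the triggering event and its resolution are recorded and reported.
- A reader might infer that such loss can occur only in the rTMS group. The termination list covers every subject, so women in Part A alone can be withdrawn for an adverse event too. Only device-related events and the mania rule are specific to Part B.
- In the mania paragraph, the study may mean Part B alone: the same paragraph says women with bipolar disorder were excluded from the study, yet that exclusion is listed only for Part B. On this reading Part A visits would go on. The wording does not settle it, and the day 22 and 29 visits would still be lost.
- The consent pages, the monitoring plan and the operating procedures are not available here and may address follow-up after withdrawal.

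What remains is that the Protocol has no status for a woman whose rTMS has stopped but who is still followed, and that its adverse event rules tie later capture to enrolment and visits.

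**Conclusion.** The point holds in a limited form. Withdrawal from the study is the only individual exit the Protocol describes. For a woman so withdrawn, the day 22 and 29 assessments, Part A visits and later maternal adverse event capture end under the stated rules. For her delivery and neonatal records, and for her place in the rTMS group, the defect is silence, not a rule to discard.

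Each woman is 10% of the Part B group, and one uncollected adverse infant outcome would turn 1/10 into 0/9. That illustration assumes one infant per woman and that the record is in fact not obtained, which the documents do not say. The withdrawal rates are also assumed. This is a cheap improvement worth making before data are lost; it does not show that the safety conclusion will be wrong.

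**What to change.** In *Termination of Study Participation* and in the mania paragraph of the rTMS risk section:

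1. Define *discontinued from rTMS* separately from *withdrawn from the study*.
2. State that a woman whose rTMS is stopped continues the day 22 and 29 assessments, Part A visits, adverse event follow-up, and delivery and neonatal record collection, unless she withdraws consent for these.
3. In the Part B statistical section of both documents, place every woman who received at least one rTMS session in the rTMS group for the safety summary, neonatal review and neonatal comparison.

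The clinical grounds for stopping rTMS are left as they are. The visits and record review are already scheduled, so the cost is a few sentences, a matching consent sentence if none is present, and a little follow-up of women who have stopped treatment.
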